15.8. Secondary Objective (Feasibility)

For the participants, the AIM and IAM will be administered at 6 months. Descriptive statistics will be presented for each instrument means and standard deviations (SD) will be reported for approximately symmetric distributions, and medians and interquartile ranges (IQR) for skewed distributions. No formal statistical hypothesis testing is planned.

For healthcare practitioners and leaders, the AIM, IAM, and FIM will be administered at baseline and at 6 months. Each measure will be summarised using means and SD when the distribution is approximately symmetric; otherwise, medians and IQR will be reported. Change scores between the baseline and 6-month assessments will be calculated and reported descriptively.

Feasibility of Intervention Completion will be calculated as the number of participants who agreed to participate, provided informed consent, were allocated to the active treatment, and completed the intervention as planned, divided by the total number of participants who provided informed consent.

No formal statistical hypothesis testing will be conducted.

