8. OBJECTIVES AND OUTCOME MEASURES

Table 1. Objectives and outcome measures

| Objectives | Outcome Measures | Timepoints of evaluation |
|--|---|--|
| Primary Objective Evaluate the effectiveness of DD+ intervention for improving QoL of patients with co-existing physical and mental NCDs in Colombia. | Change in QoL at 6 months measured by MANSA. | - Baseline Assessment -6-month follow-up- |
| Secondary Objective (Implementation) Analyse the implementation context for DD + intervention for patients with co-existing physical and mental NCD to improve their QoL in local Colombian contexts. Through the following specific objectives: 
 - Identify barriers and facilitators for implementation of DD + intervention for patients with physical and mental NCD to improve their QoL in local Colombian contexts. - Assess the feasibility of DD+ intervention for | 
 - Barriers and facilitators for implementation through qualitative interviews. - Feasibility measured through qualitative interviews. - Feasibility of Intervention Measure (FIM) - Feasibility measured as completion proportion (participants who agreed to participate, consented to do so, and were allocated to active treatment and completed the intervention as planned in relation to all those who agreed to participate and consented to do so) - Appropriateness measured through qualitative interviews. - Intervention Appropriateness Measure (IAM) | - Baseline Assessment -6-month follow-up- |

| | | |
|---|---|---|
| 
patients with physical and mental NCD to improve their QoL in local Colombian contexts.
 
 - Assess the Appropriateness of DD + intervention for patients with physical and mental NCD to improve their QoL in local Colombian contexts. - Assess the acceptability of DD + intervention for patients with physical and mental NCD to improve their QoL in local Colombian contexts. - Assess the adoption of DD + intervention for patients with physical and mental NCD to improve their QoL in local Colombian contexts. - Assess the fidelity of DD + intervention for patients with physical and mental NCD to improve their QoL in local Colombian contexts. | 
 - Acceptability measured through qualitative interviews. - Acceptability of Intervention Measure (AIM) | |

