10. STUDY DESIGN

10.1. General Design

To assess the effectiveness and implementation context of DD+, we will conduct a Hybrid I Randomised Controlled Trial (RCT) using a mixed-methods approach (11,12,40). A health economic analysis will also be included to evaluate the cost of delivering the intervention in the local setting. Effectiveness will be assessed through an RCT, implementation will be evaluated through a descriptive mixed-methods implementation study, and cost-effectiveness will be assessed through an embedded health economic analysis.

Patients in selected HC (Health Centres) will be pre-screened for chronic physical and mental health conditions. Those who meet the initial criteria will be recruited. After accepting to participate and signing informed consent, they will undergo full screening for physical and mental health conditions and QoL. Patients with co-existing physical and mental NCD will be randomised to the active intervention or the control group. Healthcare practitioners (contracted research study professional/staff) trained in DD+ will deliver the assigned intervention to each active intervention participant once per month for six months. Participants allocated to the control group will continue their usual or routine care as established by the HC professionals and procedures. Participants in the control group will be contacted periodically by phone (**Figure 1**).

[figure not shown]
Participants in both study arms will be assessed for outcome measures at baseline, 6, and 12 months. **Table 2** displays the timing and content of study procedures, including interventions, assessments, and interviews across all study visits.

To assess the **implementation context**, a mixed-methods approach will be used, with the following steps:

- a) At the 6-month assessment, all patients in the intervention arm will complete the AIM and IAM scales.
- b) At the 6-month assessment, a subsample of the intervention group participants will be invited to individual interviews to enhance explanatory power and to assess additional implementation criteria, including fidelity, adoption, and feasibility.

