12.7. Randomisation

The unit of randomisation will be the individual participant. Site-stratified blocked randomisation, with a variable block size ranging from two to four, will be performed on a rolling basis during the recruitment period. A randomisation schedule will be defined for each health centre (study site). Within each stratum, participants will be randomised in a 1:1 ratio to either DD+ or the control group. Randomisation will be performed using REDCap or via a phone call, following the corresponding randomisation schedule.

Figure 3. Study Randomisation Summary

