| Acceptability of Intervention Measure (AIM) - Score | Interval | Comprises 4 items assessing the acceptability of an intervention: approval, appeal, liking, and welcoming of the intervention. Each item is rated on a 5-point Likert scale: 1 (Completely disagree) to 5 (Completely agree). Total score is calculated by averaging the item scores. | Baseline, 6 months |
| Intervention Appropriateness Measure (IAM) - Score | Interval | Comprises 4 items assessing the perceived appropriateness of the intervention: whether it seems fitting, suitable, applicable, and a good match. Rated on a 5-point Likert scale: 1 (Completely disagree) to 5 (Completely agree). Total score is calculated by averaging item scores. | Baseline, 6 months |
| Feasibility of Intervention Measure (FIM) - Score | Interval | Comprises 4 items assessing the feasibility of the intervention: whether it seems implementable, possible, doable, and easy to use. Items are rated on a 5-point Likert scale: 1 (Completely disagree) to 5 (Completely agree). Scores are averaged across items to obtain a total score. | Baseline, 6 months |
| Feasibility of Intervention Completion | Ratio | Feasibility was measured as the proportion of participants who agreed to participate, provided informed consent, were allocated to the active treatment, and completed the intervention as planned, relative to all those who initially agreed to participate and consented. | 6 months |
| Death status | Nominal | Has the individual passed away by the end of the follow-up period? (Yes/No). This is essential for determining the QALY value, as it implies a quality-of-life value of 0 for that individual. | 12 months |
| Costs of health service use, medication and productivity lost. Out-of-pocket expenses. | Ratio | In the CSRI instrument, we collect participants' use of inpatient hospital service, use of health care services, current medication, family support, out-of-pocket expenses and employment. | Baseline, 6 months, 12 months |
| Costs of DIALOG+, and costs of supervision and training to health professional | Ratio | The Health Economics Inventory forms | Training phase, implementation and monthly in the intervention arm. The research team will calculate costs. |

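### The completion proportion for DD+ is divided by everyone who consented, so controls cap it at about 50% and screen failures pull it lower

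*Protocol*

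**What the plan says.** Section 15.8 counts the consenting participants assigned to DD+ who "completed the intervention as planned, divided by the total number of participants who provided informed consent". Table 7 (Section 15.1) states the proportion "relative to all those who initially agreed to participate and consented", and Table 1 (Section 8) describes those who "completed the intervention as planned in relation to all those who agreed to participate and consented to do so". The Synopsis carries the same definition. None of the four places limits the denominator to the DD+ arm.

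Two design features decide who falls into that denominator:

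- **Allocation.** Section 12.7 states that "participants will be randomised in a 1:1 ratio to either DD+ or the control group". Controls continue routine care and are not offered DD+ (Sections 10.1 and 12.9).
- **Order of consent and screening.** Section 10.1 says of recruited patients: "After accepting to participate and signing informed consent, they will undergo full screening for physical and mental health conditions and QoL". Sections 12, 12.3 and 12.10 (Visit 1) give the same order, and Visit 1 makes a MANSA score of 5 or less a condition for going on.

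Section 15.8 plans description only for this objective, without hypothesis tests. No target, benchmark or progression rule is attached to the proportion.

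**The concern.** A completion proportion should answer one question: of those offered the intervention, how many finished it? Here the denominator also holds two groups who were never offered it, the control arm and the people who consented but were then found ineligible. Neither group's absence from the numerator says anything about whether DD+ can be delivered.

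Section 4 of the protocol describes feasibility as a property of an intervention in a setting. The allocation ratio and the screening yield are properties of the trial. A figure driven by all three cannot be read as completion, and it cannot be compared across sites whose screening yield differs. It is listed in the Synopsis among the implementation outcomes. It is also the only feasibility number that comes from patients, because patients do not complete the FIM (Table 6). A reader who takes its name at face value would understate completion by half or more.

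**Working it through.** **Inputs from the protocol**

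- Planned sample: 226, 113 per group (Section 15.2).
- Allocation 1:1, in site-stratified blocks of two to four (Section 12.7).
- Number of centres: 15 (Section 15.11.4).
- Completion proportion: as defined in Section 15.8.

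**Input not in the protocol (assumption).** *s* is the share of consenters who are not randomised, varied from 0% to 60%.

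**Step 1. The plan's own sample size.** The protocol states no expected value for the completion proportion, so the figure to reproduce is the arm size. With SD 0.9, correlation 0.4, difference 0.4, 90% power and two-sided 5%:

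n per arm = 2 × (1.960 + 1.282)² × 0.9² × (1 − 0.4²) / 0.4² = 89.4, rounded up to 90.

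Allowing for 20% attrition, 90 / 0.8 = 112.5, rounded up to 113, or 226 in total. This agrees with Section 15.2.

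**Step 2. Formula for the reported figure.** Let *c* be the share of the DD+ arm that completes. Then

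reported proportion = (c × 113) / [226 / (1 − s)] = 0.5 × c × (1 − s).

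The factor 0.5 is the allocation ratio and (1 − s) is the screening yield. Only *c* is completion.

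**Step 3. Numbers put in.**

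| Assumed s | Consenters, 226/(1 − s) | c = 100% | c = 80% | c = 60% |
|---|---|---|---|---|
| 0% | 226 | 50% | 40% | 30% |
| 10% | 251 | 45% | 36% | 27% |
| 20% | 282.5 | 40% | 32% | 24% |
| 30% | 323 | 35% | 28% | 21% |
| 40% | 377 | 30% | 24% | 18% |
| 50% | 452 | 25% | 20% | 15% |
| 60% | 565 | 20% | 16% | 12% |

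The first row needs no assumption about screening. The other rows are illustrations.

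**Step 4. How firm is the 50%?** It is exact at 113:113. Section 12.7 specifies "Site-stratified blocked randomisation, with a variable block size ranging from two to four", so an unfinished block could leave up to two extra DD+ participants at a site. In the extreme case that this happens at all 15 centres, the DD+ arm has (226 + 30)/2 = 128 participants, and the ceiling with no screen failures is 128/226 = 56.6%. A screen-failure share above 1 − 113/128 = 11.7% would bring even that case below 50%.

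**Step 5. Comparison between sites (screen-failure rates assumed).** A site where 50% of DD+ participants complete and 10% of consenters fail screening reads 0.5 × 0.50 × 0.90 = 22.5%. A site with 80% completion and 50% screen failure reads 0.5 × 0.80 × 0.50 = 20%. The site with worse completion shows the higher figure.

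**Step 6. With the DD+ arm as denominator.** The proportion is c × 113/113 = c. It runs from 0% to 100% and depends on neither the allocation ratio nor *s*.

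**The case against.** The best defence is that this is a deliberate measure of flow from consent to completion. That could justify keeping screen failures in the denominator. It does not justify keeping controls there, because they are excluded by the randomisation and not by any difficulty in delivering DD+. The variable is also named for completion of the intervention.

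Several limits on the point do stand:

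- The outcome is secondary and descriptive, in a design whose primary aim is effectiveness. No decision depends on its value.
- The screen-failure part is less certain than the control-arm part. No rate is given, and the protocol's use of the word participant varies around screening: Sections 12 and 12.3 call people at that stage potential participants, while Visit 1 in Section 12.10 calls them participants once they have consented. The literal reading of the denominator includes screen failures, but only the dilution by controls is beyond dispute.
- The within-arm rate can be recovered at reporting. Arm sizes will be known, and attendance at the six intervention visits has to be recorded to classify adherence for the interview sample (Section 13.3.1).

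A reader might go further and infer that the measure would make a workable intervention look infeasible, or that the trial could then say nothing useful about scale-up. The documents do not support either. No value on this scale is labelled as failure. Feasibility is also assessed by FIM scores from leaders and DD+ providers and by interviews, including 24 patients. The data for the proper rate will exist.

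**Conclusion.** The definition is wrong as written, and it is a fixed formula repeated in four places, not a slip in one. Followed exactly, it gives a figure capped at about 50% by the control arm alone (113/226 at the planned split). Screen failures lower it by an amount that cannot be calculated from the protocol: to 35% or 25% at full completion if 30% or 50% of consenters fail screening, both assumed. What is reported is completion multiplied by the allocation share and by the screening yield.

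This should be fixed, but it is not critical. The primary analysis and the sample size are untouched, nothing is tested on this outcome, and no data would be lost. The 50% ceiling rests on near-equal arms; every figure below it at full completion rests on an assumed screen-failure rate.

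**What to change.** In the Synopsis, Table 1, Table 7 and Section 15.8, change the denominator to participants randomised to DD+ and leave the numerator as it is. Report two further proportions separately, labelled as recruitment yield: consented to eligible, and eligible to randomised. The information now folded into the consent-based denominator is then kept, but apart from completion. A 95% confidence interval would help the reader but is optional, since the plan is descriptive.

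The new denominator does not settle what counts as completing as planned. If the statistical analysis plan does not already define that, it is the natural place to do so.

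The cost is one definition edited in four places. It needs no new data, no change to the case report form and no change to the sample size.

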15.9. Secondary Objective (Effectiveness)

Mixed-effects models will be used to evaluate the effect of the intervention on the secondary outcomes (see **Table 1**) at 6- and 12-month follow-up assessments. Analyses will be conducted under the intention-to-treat principle. Each model will include fixed effects for treatment group (intervention vs control), time, the baseline score of the corresponding outcome, and other relevant baseline covariates. A random effect for clinical professional group (cluster) will be included to account for intragroup correlation. The models will report adjusted mean differences between groups, with corresponding 95% confidence intervals (CIs) and p-values.

15.10. Software

All primary and secondary analyses will be performed using R statistical software (R Foundation for Statistical Computing) (52), via the RStudio interface (53).

15.11. Health Economics Analysis

15.11.1. **Measurement of health economic data**

Resource use specific to DD+ will capture both start-up (training, initial supervision, and device setup) and steady-state delivery (clinician time per DD+ session and documentation, routine/top-up supervision, app/support). These data will be obtained from site time sheets/logs and finance records in a health economics inventory form.

All other healthcare and patient-level resource use (whether under DD+ or usual care) will be collected at baseline, 6 months, and 12 months using a custom, interview-based health-economics inventory (CSRI-style) tailored to primary care for patients with co-occurring physical and mental NCDs in Colombia. Total cost per participant will be computed for 0–6 and 0–12 months from the health-system perspective.

15.11.2. **Value of resource utilization**

The amount of resource usage for each cost element will be combined with the relevant unit costs. Hourly trainer clinician wage rate will be used as the unit cost to calculate costs to training sessions and supervision, transportation expenses will be included in the implementation phase. On the other hand, hourly Health professional wage rates will be used to calculate the cost of their training, documentation and deliver DIALOG+. Unit costs for other health care services such as visits to a general practitioner, nurse, nutritionist, phycologist, social worker, psychiatrist, internal medicine or other subspecialist, and hospitalizations will be obtained from the tariff manual ISS 2001 + 30% and hospital bills (for sensibility analysis). The unit cost of the current medication prescribed to patients will be sourced from the Colombian drug price information system (SISMED in Spanish) based on the weighted price of each medication for the year. Costs will be reported in U.S. dollars (USD), using the average representative market exchange rate published by the Central Bank of Colombia (*Banco de la República*) for the study year. Sensitivity analyses will explore the impact of applying the minimum and maximum values of this exchange rate within the same year.

15.11.3. **Discounting**

No discount rate will be applied because the time horizon is 12 months.

15.11.4. **Geographical Jurisdictions**

The study will be carried out separately in 15 centers of Colombia.

15.11.5. **Measurement of effectiveness outcomes for health economic evaluation**

For the economic evaluation EQ-5D-5L will be the primary outcome. The EQ-5D-5L describes health on 5 dimensions (mobility, self-care, usual activities, pain/discomfort, anxiety/depression), each with 5 levels, yielding 3,125 possible health states denoted by a five-digit code (e.g., 11223). These health-state profiles are converted to utility weights using a Latin American value set; utilities are anchored at 1 = full health and 0 = dead, with negative values allowed for “worse-than-dead” states. This enables QALY estimation. EQ-5D-5L will be collected at baseline, 6-months and 12-months after randomisation.

There is no published Colombia-specific EQ-5D-5L value set. Therefore, in this trial we will use a Latin American value-set strategy: the Peru EQ-5D-5L value set for the base case, with Uruguay EQ-5D-5L and England EQ-5D-5L in sensitivity analyses to test robustness to the choice of tariffs.

Utilities will be assigned to each participant's EQ-5D-5L state at baseline, 6 months, and 12 months, and QALYs over 12 months will be computed using the area-under-the-curve (trapezoidal) method with linear interpolation between time points. Guidance on analysis and reporting follows (54).

15.11.6. Analysis of population and missing data

The economic analysis set will include all randomised participants, in line with the intention-to-treat (ITT) principle. Missing data on costs and other outcome variables in the health economic analysis will be examined. Mean imputation and multiple imputation methods will be applied to address missing data.

15.11.7. Analysis of cost-effectiveness

We will compute the ICER as the additional cost per additional QALY gained ($\Delta C/\Delta E$). Interpretation will use Colombia-relevant willingness-to-pay (WTP) benchmarks. Specifically, we will present cost-effectiveness acceptability curves (CEACs) across a WTP range and highlight the empirically estimated Colombia threshold of about US\$5,181 per QALY (\approx COP 17 million in 2019 prices) from Espinosa et al. (55) (IETS) updated to the study price year (2025) using DANE CPI. DIALOG+ will be described as cost-effective when the ICER lies below a WTP value deemed acceptable in Colombia, and we will report the probability of cost-effectiveness at the updated reference threshold and other policy-relevant WTP points.

Differences between trial arms in costs and outcomes will be estimated on an intention-to-treat basis, initially unadjusted and subsequently adjusted for pre-specified baseline covariates. If participant characteristics differ systematically between arms, adjusted models will include age, sex, NCD condition group (hypertension/obesity/T2DM), mental health condition group (anxiety, depression or alcohol misuse), baseline utility (EQ-5D-5L), baseline MANSA and WHOQOL-BREF, baseline total cost, and site (fixed effects).

Incremental costs will be estimated using mixed-effects generalized linear models appropriate for skewed data (primary: Gamma family with log link, or log-normal), including by random effect in the model for healthcare practitioners who delivered DIALOG+ considering clusters. Incremental cost-effectiveness will be estimated with linear mixed models including the same covariates.

Based on the results for quality of life, blood pressure control, glycated hemoglobin, and within-trial cost-effectiveness, we plan to conduct a modeled cost-effectiveness extension study over a 5-year time horizon from the healthcare perspective. In addition, a budget impact analysis with the same horizon will be carried out to support acceptability among decision-makers in the country.

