15.2. Sample Size Determination

The sample size calculation for this study will be based on parameters derived from previous DIALOG+ trials (35). A standard deviation of 0.9 for the MANSA and a correlation of 0.4 between baseline and follow-up measurements will be assumed, while an effect size of 0.4 points on the MANSA will be considered the minimal clinically important difference (MCID) for quality of life in this patient population. Based on these parameters, a total of 90 participants per group will be required to achieve 90% power at the 5% two-sided significance level. To account for an anticipated 20% attrition rate, the final sample size will be set at 226 participants (113 per group).

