15.11.8. Sampling uncertainty

Sampling uncertainty around the ICER will be quantified using cost-effectiveness planes and cost-effectiveness acceptability curves (CEACs). CEACs will report the probability that DIALOG+ is cost-effective across a range of willingness-to-pay (WTP) values per QALY relevant to Colombia. We will highlight

Colombian specific WTP benchmarks (e.g., values referenced by IETS and recent empirical estimates) and present results at the study price year.

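### The cost-effectiveness rule in Section 15.11.7 (ICER below the WTP value) is valid only for a QALY gain; with a QALY loss it gives the reverse of the correct label, and the protocol sets no such condition

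*Protocol*

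**What the plan says.** Cost-effectiveness is a secondary objective (protocol, Section 8, Table 1). In Section 15.11.7 the ratio is defined first: "We will compute the ICER as the additional cost per additional QALY gained", written as ΔC/ΔE. The rule for the conclusion follows: "DIALOG+ will be described as cost-effective when the ICER lies below a WTP value deemed acceptable in Colombia". The same paragraph plans to "highlight the empirically estimated Colombia threshold of about US\$5,181 per QALY", updated to the study price year. The sentence holding the rule goes on: "we will report the probability of cost-effectiveness at the updated reference threshold and other policy-relevant WTP points".

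Section 15.11.8 assigns cost-effectiveness planes and acceptability curves (CEACs) to sampling uncertainty around the ICER. It does not say how the CEAC probability is computed.

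Nowhere in Section 15.11 is there a condition on the sign of ΔE or ΔC, a rule for dominance, or a net-benefit criterion.

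**The concern.** A ratio loses the signs of its parts. A DD+ that costs more and loses QALYs has a negative ICER, as does a DD+ that saves money and gains QALYs. Both lie below every positive WTP value, so the rule gives the worst and the best result the same label.

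Neither sign is ruled out here. On cost, "Resource use specific to DD+ will capture both start-up (training, initial supervision, and device setup) and steady-state delivery" (Section 15.11.1), so a positive ΔC is likely. On effect, "QALYs over 12 months will be computed using the area-under-the-curve (trapezoidal) method with linear interpolation between time points" (Section 15.11.5), and nothing restricts the sign of the difference between arms. The sample size was set on MANSA, not on QALYs (Section 15.2). If the true QALY difference is small, a negative estimate is an ordinary outcome.

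At stake is the label attached to the cost-effectiveness objective, which also feeds the 5-year model and the budget impact analysis announced in Section 15.11.7.

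**Working it through.** **Inputs from the protocol.** Rule: cost-effective if ΔC/ΔE < λ. Reference threshold: λ = US$5,181 per QALY before the price update (15.11.7). Analysed number: 90 per group (15.2).

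**The plan's own figures.** The threshold is an external estimate and cannot be derived from the protocol. Its two currency values imply 17,000,000 / 5,181 ≈ 3,281 COP per USD, and no exchange rate is given to check this. The 90 per group reproduces: 2 × (1.960 + 1.282)² × 0.9² × (1 − 0.4²) / 0.4² ≈ 89.4, rounded up to 90; and 90 / 0.8 = 112.5, rounded up to 113. It is used below only as the number per arm.

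**Algebra.** The standard criterion is incremental net monetary benefit, NMB = λ·ΔE − ΔC > 0.
- If ΔE > 0, then ΔC/ΔE < λ is the same as ΔC < λ·ΔE, that is NMB > 0. The rule is right.
- If ΔE < 0, multiplying by ΔE turns the inequality round: ΔC/ΔE < λ is the same as ΔC > λ·ΔE, that is NMB < 0. The rule gives the opposite label every time.

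**Illustrative points at λ = US$5,181** (ΔC and ΔE are chosen for illustration; the protocol gives none):

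| ΔC (US$) | ΔE (QALY) | ICER | Label by the rule | NMB (US$) | Label by NMB |
|---|---|---|---|---|---|
| +100 | +0.04 | 2,500 | cost-effective | +107.2 | cost-effective |
| +100 | +0.01 | 10,000 | not | −48.2 | not |
| −100 | +0.02 | −5,000 | cost-effective | +203.6 | cost-effective |
| +100 | −0.02 | −5,000 | cost-effective | −203.6 | **not** |
| +200 | −0.02 | −10,000 | cost-effective | −303.6 | **not** |
| −50 | −0.02 | 2,500 | cost-effective | −53.6 | **not** |
| −200 | −0.02 | 10,000 | not | +96.4 | **cost-effective** |

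For the fifth row: 5,181 × (−0.02) − 200 = −103.6 − 200 = −303.6. Rows three and four have the same ICER and opposite net benefits.

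**How often.** By the algebra, the share of trials misclassified is exactly P(ΔE estimate < 0). It does not depend on ΔC. The cost difference decides only whether the wrong label is a false claim or a false rejection; when ΔC > 0 it is always a false claim.

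Assumption, not in the protocol: QALY SD 0.18. Then SE(ΔE) = 0.18 × √(2/90) ≈ 0.0268, and P(ΔE estimate < 0) = Φ(−true ΔE / SE):

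| True ΔE | z | Share misclassified |
|---|---|---|
| +0.03 | −1.12 | 13% |
| +0.02 | −0.75 | 23% |
| 0 | 0 | 50% |
| −0.02 | +0.75 | 77% |

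At true ΔE = 0 the share is 50% whatever the SD. At true ΔE = +0.02 it runs from about 9% (SD 0.10, SE 0.0149) to about 25% (SD 0.20, SE 0.0298).

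**The case against.** The best defence is that the definition speaks of a QALY *gained*. If DD+ loses QALYs, the quantity as worded does not exist, and an ICER below the WTP value is ordinary shorthand for the case of a gain. The planned plane would show the quadrant at once, and a probability of cost-effectiveness is reported beside the label. A careful analyst would probably not call a dominated DD+ cost-effective. It can also be said that net-benefit formulae and dominance labels usually belong in an analysis plan that is not shown here.

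Much of this stands as mitigation. It lowers the chance of a false statement in the final report, but it does not repair the rule. The word *gained* describes the ratio and does not say what to conclude when QALYs are lost. The plane and the CEAC are assigned to sampling uncertainty, while the label rests on the ICER alone. Nor is this detail left for later: the protocol states the decision rule and leaves out the condition that it needs.

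Two stronger readings are tempting. A reader might infer that the trial will declare a harmful DD+ cost-effective. The documents do not support that, because the plane is planned and a point estimate of −0.02 lies within one assumed SE of zero, so it would not show harm. A reader might also infer that the CEAC is wrong too or, conversely, that it already rests on net benefit and so protects the conclusion. The protocol supports neither, since it does not define the calculation. If the CEAC were computed as the share of replicates with ICER below WTP, it would inherit the fault; that is a risk only.

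**Conclusion.** Wrong as written, of moderate weight. For every ΔE < 0 the rule in Section 15.11.7 gives the opposite of the net-benefit label. This is arithmetic and needs no assumption about the trial.

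How often it would bite does rest on assumptions: 50% of trials if the true ΔE is 0, and about 13% to 77% for true ΔE from +0.03 to −0.02, with a QALY SD of 0.18 and 90 analysed per arm. These are rates under literal application of the rule, not forecasts of what the report will say.

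The objective is secondary. The fault touches no data collection, neither randomisation nor sample size, and not the MANSA analysis. The label can be recomputed from the same ΔC and ΔE.

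**What to change.** In Section 15.11.7, replace the rule with: *DD+ will be described as cost-effective when the incremental net monetary benefit, λ·ΔE − ΔC, is greater than 0 at the updated reference threshold λ. An ICER will be reported only when ΔE > 0 and DD+ is not dominant; otherwise the result will be named as dominant, dominated, or cost-saving with QALY loss.*

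In Section 15.11.8, add: *The CEAC gives, at each WTP value, the probability that the incremental net monetary benefit is greater than 0.*

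The cost is two short text changes, with no new data and no new models. Making them before results are known avoids a post hoc change to the rule for the conclusion.
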